IDENTIFYING MARKERS OF TRAJECTORY IN PEDIATRIC COMPLEX REGIONAL PAIN SYNDROME

PROTOCOL

Principal Investigators:

[name]

Date: July 12, 2018

SYNOPSIS

Title	Identifying markers of trajectory of short-term and long-term recovery in pediatric complex regional pain syndrome (CRPS)
Study Objectives	Characterize neurological and psychosocial markers of trajectory of recovery in pediatric CRPS.
Significance	
 1. CRPS is a severe and complex chronic pain condition in children. 2. Many psychosocial factors impact its development and recovery. 3. CRPS has a strong central component, which is reflected by structural and functional changes in the brain. 4. The interaction between these cerebral changes and recovery has been seldom investigated to date. 5. Interactions between cerebral changes and psychosocial factors, which might affect recovery, are unknown.
Study Design	Basic science investigation of children with CRPS undergoing outpatient and inpatient treatments at CCHMC and of healthy children.
Primary Aim	To characterize markers that are predictive of trajectory of recovery in CRPS patients
Sample size	63 youth/parent dyads
Study Duration	Two years of data acquisition, unlimited analyses
Inclusion Criteria	
All Children:
 
 – Age between 10 and 17 years old – Fluent in English

Inpatients:

- Diagnosis of CRPS
- Former unsuccessful treatment for CRPS
- Scheduled for or beginning the usual inpatient treatment for CRPS at the FIRST clinic at CCHMC.

Outpatients:

- Diagnosis of CRPS
- Scheduled for or beginning the usual outpatient treatment for CRPS at the pain management clinic

Healthy children:

- No diagnosis of chronic pain.

Parents:

- Fluent in English
- Child participating in the study

Exclusion criteria

All child participants:

- Weight/size incompatible with MRI scanner
- Identification of brain, neurologic, or severe psychiatric abnormalities beyond those normally associated with chronic pain.
- Documented developmental delays or impairment
- Any MRI contra-indication, including
 - Braces, stents, clips, pace-maker or other metal implants affecting the safety of the participants in the scanner and/or the quality of the images
 - pregnancy
 - claustrophobia

TABLE OF CONTENTS

1	SPECIFIC AIMS	6
1.1	SPECIFIC AIM 1	6
1.2	SPECIFIC AIM 2	7
1.3	SPECIFIC AIM 3	7
2	BACKGROUND INFORMATION	7
2.1	BACKGROUND	7
2.2	PRIOR STUDIES	9

Pediatric Complex Regional Pain Syndrome (CRPS) is a severe and complex type of pediatric chronic pain, which impacts majorly the children's and their families' lives (McClain & Suresh, 2011). CRPS is divided into Type I and Type II, which are differentiated by the absence (Type I) or presence of a discreet nerve injury (Type II) (Harden et al., 2010). CRPS is treated, in the first instance, with outpatient multidisciplinary interventions (Carter & Threlkeld, 2012; Dickson, 2017; Katholi, Daghstani, Banez, & Brady, 2014; Maihöfner, Seifert, & Markovic, 2010). However, several psychosocial factors, such as pain catastrophizing, depression, and/or familial environment, can affect pain symptoms and recovery (Bruehl & Chung, 2006; Cruz, O'Reilly, Slomine, & Salorio, 2011; Vervoort, Trost, & Van Ryckeghem, 2013). In such cases, more intensive interventions necessitating hospitalization are necessary to help the patients (Dickson, 2017). Defining which factors predict the trajectory of recovery could allow for better targeting of the treatment that a patient needs to successfully recover. In this study, the effect of psychosocial and sensory factors and possible brain markers predicting changes in pain symptoms before – after treatment will be investigated in children diagnosed with CRPS and currently undergoing the usual inpatient or outpatient treatment at CCHMC. In addition, brain changes before – after treatment will be analyzed, as well as potential psychosocial influences on these changes. To establish a baseline of changes associated with CRPS recovery, potential psychosocial and sensory markers, as well as brain activation and connectivity in CRPS patients will be compared to healthy children. To assess the psychosocial environment, parents of children enrolled in the study will complete a series of questionnaires.

For this purpose, we define the following specific aims to investigate in a main study:

1.1 Specific aim 1

Identify changes in psychosocial, psychophysical, sensory, and cerebral characteristics associated with CRPS.

Psychosocial, psychophysical, sensory, and cerebral measurements in children diagnosed with CRPS will be compared with such measurements in healthy children before or at the beginning of an inpatient or outpatient treatment at CCHMC.

We hypothesize that children diagnosed with CRPS will differ from healthy children in their responses to psychosocial, psychophysical, sensory, and cerebral measurements.

1.2 Specific aim 2

Develop predictors of short-term and long-term recovery from CRPS using psychosocial measures, sensory sensitivity, and brain function and structure.

Changes in symptoms of CRPS, such as pain and functional disabilities, will be investigated in relation to potential psychosocial, sensory, and brain markers. Variables obtained at baseline will be examined for significant relationship with recovery.

1.3 Specific aim 3

Investigate the evolution of changes in psychosocial, psychophysical, sensory, and cerebral measures, associated with CRPS.

Short-term and long-term changes in psychosocial, psychophysical, sensory and cerebral measures in children diagnosed with CRPS will be compared to changes in healthy children.

We hypothesize that differences in psychosocial, psychophysical, sensory and cerebral measures between children with CRPS and healthy children will be reduced immediately after treatment, as well as six-month post treatment.

2 Background information

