5.1 Statistical plan

5.1.1 *Analyses of neuroimaging data*

All structural and functional image data will be primarily processed by the FSL software package (FMRIB Software Library, Oxford, UK). Such processing will generally include motion correction, co-registration of structural and functional data, transformation of structural data to standard space, temporal and spatial filtering, image segmentation, and tractography. Other packages such as CONN, SPM, AFNI, FreeSurfer, and others may be used to augment image processing. Functional and structural data will be statistically analyzed using both parametric and non-parametric approaches, independent component analyses, in addition to multivariate pattern analysis. In general, fixed effects statistical models will be used for within-participants components of analyses, while random effects models will be used for between participant's components. These statistical analyses will generally be executed within FSL or similar software packages developed or adapted for analyses of functional and structural data.

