5.2 Number of participants to be enrolled

A total of 63 participants, i.e. 21 participants per group, will be enrolled in this study. Power calculations were performed for both imaging data and behavioral data to ensure an adequate sample size to detect changes in brain activity and interpret them in the context of behavioral effects.

Neuroimaging

Power calculations for neuroimaging data are challenging since such calculations depend crucially on effect size as well as properties of the imaging data and statistical approach used to deal with the multiple comparisons of >20,000 voxels. As no data is accessible so far in youth with CRPS, we used the NeuroPower tool to calculate statistical power and sample sizes based on our preliminary ASL data in youth with migraine, which study had a similar design to the one described here. Within-subject power calculations of ASL activation differences indicate that 19 participants per group would be required for 80% power with this imaging modality for treatment related changes in activity within group. All comparisons were calculated using z-transformed statistical images of the whole brain, a cluster-forming threshold of $z > 3.1$ and $p < 0.05$, isotropic smoothness of 5mm (8mm for ASL), and voxel sizes of 2x2x2mm, and a Gaussian Random Field theory-based approach for multiple comparisons. For these complex data, statistical power is defined as an 80% probability of correctly detecting an active peak for all peaks above the cluster-forming threshold.

Behavioral and psychophysical sample size estimation

We used G*Power to perform a power analysis for our behavioral data. This calculation resulted in an overall number of participants of 54, i.e. 18 participants per group, to achieve a small effect size f of 0.25 (Cohen, 1988) with a type I and II errors at 5%. An additional 15% has been added to that result to account for incomplete dataset due to participants' withdrawal and equipment failure. This number is consistent with that proposed for fMRI.

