7.5 Risk/benefit ratio and importance of the information to be obtained

The risk/benefit ratio is favorable for this study. There is no anticipation of adverse events. The risk encountered by the participants and their parents is minimal because all procedure can be terminated immediately.

There will be no direct benefit for the participants, but the results of this project are important for our understanding of underlying mechanisms of chronic pain and of response to treatment. Ultimately, this will help improve treatment, especially by improving the prognosis of the most adequate treatment for each patient.

8 Funding

Acquisition and analyses of data is funded by the [name] family donation for research on CRPS and by startup funds provided by the Department of Anesthesiology.

9 Reimbursement for studies

This is a study on markers of trajectory in pediatric CRPS. Although measures will be taken before and after treatment, this study does not depend on treatment of CRPS. Therefore, treatment will not be covered by the researcher.

Children enrolled in this study will receive a payment up to \$120 per session to compensate any inconvenience associated with their participation in this study. This amount includes a payment of \$20 for the completion of the questionnaires, \$50 for quantitative sensory testing, and \$50 for the MRI scan. Similarly, parents will receive a payment of \$20 per session for the completion of questionnaires. Payment will be proportional to the activities and sessions completed by the participants.

10 Bibliography

Bastien, C. H., Vallières, A., & Morin, C. M. (2001). Validation of the Insomnia Severity Index as an outcome measure for insomnia research. *Sleep Medicine*, 2(4), 297–307.

Berry, J. O., & Jones, W. H. (1995). The parental stress scale: Initial psychometric evidence. *Journal of Social and Personal Relationships*, 12(3), 463–472.

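### Aim 2 sets out to develop predictors of recovery from significance in the same 36 to 42 patients with no internal validation stated, so reported predictive strength is expected to be overstated

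*Combined protocol and SAP*

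**What the plan says.** The synopsis gives the primary aim as "To characterize markers that are predictive of trajectory of recovery in CRPS patients". Section 1.2 turns this into Aim 2, "Develop predictors of short-term and long-term recovery from CRPS using psychosocial measures, sensory sensitivity, and brain function and structure", and gives one procedure: "Variables obtained at baseline will be examined for significant relationship with recovery". Recovery means change in symptoms such as pain and functional disability, at the end of treatment and six months later.

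Section 5.1.2 says that multilevel regressions and mixed ANOVAs might be used. Section 5.1.1 lists, among its general imaging methods, "independent component analyses, in addition to multivariate pattern analysis", without a procedure and without linking it to Aim 2. Section 5.3 sets significance at p<0.05, with cluster-based control for whole-brain maps. Section 5.4 includes everyone whose data pass quality assurance.

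On size, section 5.2 states: "A total of 63 participants, i.e. 21 participants per group, will be enrolled in this study". The behavioural calculation behind it "resulted in an overall number of participants of 54, i.e. 18 participants per group", for what the plan calls a "small effect size f of 0.25". Neither this nor the imaging calculation is a sample size for prediction.

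**The concern.** A marker chosen because it is significant in a small sample has, on average, a larger correlation in that sample than in the population. If the same patients then supply the estimate of how well it predicts, the estimate carries that excess. Multiplicity is a separate matter. Multiplicity concerns false markers, whereas here the strength of a true marker is also overstated, and a stricter threshold makes that worse.

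The stake is the conclusion of the primary aim. A set of markers could appear to explain a useful share of recovery and yet predict new children no better than the group average. Section 7.5 hopes that the work will in time help with "improving the prognosis of the most adequate treatment for each patient", a use for which in-sample association is not evidence.

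**Working it through.** **1. The plan's own sample size.** Section 5.2 does not name the G*Power test. Taking a repeated-measures within-between interaction with k=3 groups, m=3 sessions, f=0.25 and alpha=0.05, and assuming a correlation of 0.5 between sessions and sphericity:

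- lambda = f² × N × m / (1 − rho) = 0.0625 × 54 × 3 / 0.5 = 20.25
- df = (k−1)(m−1) = 4 and (N−k)(m−1) = 102
- power = 0.958, and 54 is the smallest multiple of 3 that reaches 0.95

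Then 54 × 1.15 = 62.1, rounded up to 63. The figure reproduces under those assumptions, but it is a calculation for group-by-time change.

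**2. Patients available for Aim 2.** Two of the three groups have CRPS: 2 × 21 = 42 enrolled and 2 × 18 = 36 after the allowance.

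**3. Candidate markers.** The questionnaire schedule in section 3.2.4.2 lists 9 child and 9 parent instruments, 18 in all. Leaving out the FDI, which is also an outcome, gives 17. Subscales, the sensory battery on two limbs and imaging measures add more. The plan gives no total, so 17 to 28 is assumed, with 18 to 45 as a wider range.

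**4. What p<0.05 demands.** With r = t / √(t² + n − 2):

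- n=36: 2.032 / √(4.130 + 34) = 0.329, R2 0.108
- n=42: 2.021 / √(4.085 + 40) = 0.304, R2 0.093

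So even one marker is inflated if it is reported only when significant. Across n=36 to 42, a true r of 0.2 is reported on average as 0.39 to 0.41, a true r of 0.3 as 0.41 to 0.43, and a true r of 0.5 as 0.51 to 0.52.

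**5. Several markers together.** This is a simulation with assumed inputs: n=36, 17 to 28 markers inter-correlated at 0.3, each screened at p<0.05, survivors refitted in the same patients, and the model tested on 2,000 new patients. Averages are over runs in which something was selected.

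| True signal | Apparent R2 | R2 in new patients |
|---|---|---|
| None | about 0.20 | about -0.25 |
| One marker, r=0.35 (R2 0.12) | 0.26 to 0.30 | -0.07 to -0.12 |
| One marker, r=0.5 (R2 0.25), 17 markers | about 0.34 | about 0.10 |

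A negative R2 means prediction worse than the group mean. With no true marker, a model is still found in roughly half to two thirds of runs.

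**6. Brain maps, conditionally.** If z>3.1 were used as the voxel threshold for brain-recovery maps, the one-sided p is 0.00097. At n=36, t=3.36 and r = 3.36 / √(3.36² + 34) = 0.499. At n=42, t=3.32 and r = 3.32 / √(3.32² + 40) = 0.465. Peak correlations in surviving clusters would be at least about 0.46 to 0.50 whatever the true value.

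**7. Does validation recover the truth?** With uncorrelated candidates (18 to 45) and true signal, 10-fold cross-validation that repeats the screen in each fold came within about 0.04 of new-patient R2 on average. With 45 correlated candidates at n=36, the unpenalised refit was unstable: one setting averaged a cross-validated R2 of -8.1. That argues for a short candidate list or a penalised model.

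**The case against.** The strongest reply is that the simulated pipeline is not in the plan. Nothing says that significant markers will be pooled in one model, and no R2 or other performance measure is promised. That stands. A reader might infer that the study will report a model explaining a fifth or more of recovery that is in truth worse than the mean; the documents do not support so specific a forecast, and the table is an illustration.

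A reader might also infer that any brain correlation reported must be at least 0.46 to 0.50. The plan gives z>3.1 only as a setting of the power calculation in section 5.2. Section 5.3 names cluster-based methods without that value, and no section says that cluster correlations will be extracted as predictive strength. Step 6 is therefore conditional.

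Section 3.1 calls the study basic science and primarily mechanistic, and the benefit in section 7.5 is an ultimate one, so Aim 2 should not be read as building a clinical tool. But the wording of Aim 2 is still to develop predictors, and the plan does not label it exploratory.

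Section 3.1 also uses the patient-control contrast to define potentially relevant markers. That filter does not use recovery and could shorten the list: with 5 candidates and a true r of 0.5, apparent R2 was 0.31 against 0.18 in new patients. The gap is smaller but remains, and section 1.2 still screens on recovery.

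Multivariate pattern analysis is often run with cross-validation. It would be wrong to say that none will be done; the plan does not state any, and it would not cover questionnaire or sensory markers. Cluster-based control limits false-positive clusters but does not correct the size of an effect.

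**Conclusion.** The point holds as an omission with an expected, not certain, consequence. Markers are to be identified by significance in 36 to 42 patients, and no internally validated estimate is stated for any Aim 2 method. Under the assumptions in step 5, apparent R2 exceeds new-patient R2 by about 0.45 with no true marker (0.20 against -0.25) and by about 0.24 with one marker at r=0.5 among 17 (0.34 against 0.10). The gap would be small for a single strong marker chosen in advance. The number of candidates, their inter-correlation, the true signal and the screen-then-refit model are all assumed. Imaging features, two outcomes and two time points are left out of the simulation and would add to the selection. The change should be made, though it does not threaten the study's conduct.

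**What to change.** Add to section 5.1 that any claim of predictive performance for Aim 2 will rest on an internally validated estimate in the CRPS patients, by repeated k-fold cross-validation or bootstrap optimism correction. All marker selection, tuning and region definition, including those in multivariate pattern analysis, must be repeated inside each training set or resample. Report the validated estimate with an interval or a permutation p-value beside the in-sample associations. Label in-sample and cluster-extracted correlations as descriptive and needing external validation. A short pre-specified candidate list or a penalised model would help, but either is a choice for the investigators.

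The cost is SAP wording and computing time, with no new patients, visits or data. There are two downsides. Reported strength will look less favourable. The validated estimate is also imprecise at this size: the SD of cross-validated R2 across simulated trials was about 0.16 to 0.21, so it should not be read as a precise figure.

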2.1 Background

Pediatric chronic pain is an important health issue that affects up to 46% of children (McClain & Suresh, 2011). Although no clear statistics on its prevalence can be found, CRPS is a severe form of pediatric chronic pain, which is seen frequently in intensive pain treatment programs (Friedrichsdorf et al., 2016; McClain & Suresh, 2011). It has major consequences on the social and psychological well-being and development of the child, often affecting family life and school attendance (Dickson, 2017).

CRPS affects the peripheral and central systems. Peripherally, pediatric CRPS affects predominantly the lower limbs unilaterally or bilaterally (Low, Ward, & Wines, 2007). In addition, CRPS is thought to have a strong central component (Jänig & Baron, 2002). Previous studies have highlighted changes in brain activation and connectivity in patients with CRPS compared to healthy children. Such changes have been highlighted in areas previously associated with pain, such as the insula, thalamus, somatosensory cortices, as well as in the fear and reward networks, including the amygdala and basal ganglia (Erpelding, Sava, et al., 2014a; Erpelding, Simons, et al., 2014b; Lebel et al., 2008; Linnman et al., 2013; Simons et al., 2016). It remains unclear if these changes vary as a function of the severity of the CRPS symptoms. It is also unknown whether some of these changes could predict the success of treatments or the spread or worsening of symptoms.

CRPS symptoms often require treatment. Although outpatient multidisciplinary treatment is recommended as first line intervention (Katholi et al., 2014), intensive inpatient treatments are sometimes needed to achieve sufficient improvement of CRPS symptoms (Katholi et al., 2014; Logan et al., 2012). Such treatments have been associated with significant reduction in pain and functional disabilities, as well as with changes in central mechanisms underlying CRPS (Erpelding, Simons, et al., 2014b; Logan et al., 2010; Williams, Collins, Pruitt, & Rose, 2015). Although several psychosocial factors have been associated with CRPS, relatively little is known about the influence of these factors on the success of a treatment.

Psychosocial factors, such as pain catastrophizing, depression, readiness to change, family environment, and parental response to child's pain are associated with children's experience of pain (Bruehl & Chung, 2006; Carter & Threlkeld, 2012; Palermo & Eccleston, 2009; Pielech et al., 2014; Simons, 2016), suggesting a potential association of such factors in the development and the resolution of CRPS symptoms. However, to our knowledge, no study so far has investigated the relation between these factors and the severity of CRPS symptoms, as well as their impact on the success of the treatments.

Finally, sensory perception has been suggested to be altered in patients with CRPS. Hypersensitivity to visual and auditory stimuli is sometimes described by clinicians treating CRPS patients. It is so far unclear if this hypersensitivity affects multiple sensory modalities or if hypersensitivity might impact on the efficacy of the treatment for CRPS.

Sensitivity to thermal and mechanical stimuli has been previously reported as altered in pediatric CRPS. Interestingly, these alterations vary among patients (Sethna, Meier, Zurakowski, & Berde, 2007). Mechanisms responsible for such variation are not known yet, nor is it known if such a mechanism could be associated with the severity of the CRPS symptoms. Furthermore, it is not known if treatment affects these abnormalities of sensory perception.

2.2 Prior studies

Two studies performed in CCHMC have established the efficiency of multidisciplinary treatments (Lynch-Jordan et al., 2014; Williams et al., 2015). In the first study, which was conducted in the outpatient pain management clinic, pain treatment included cognitive behavioral therapy and medical treatment. In the second study, which took place in the inpatient “Functional Independence Restoration Program” (FIRST), chronic pain patients received a multidisciplinary treatment, including occupational therapy, physical therapy, rehabilitation therapy, psychotherapy, and medical treatment. Results from these studies highlight a significant reduction in pain disabilities, as well as in pain intensities in patients diagnosed with chronic pain, supporting the validity of such treatments.

The project described in this protocol will extend this knowledge by investigating psychosocial, sensory and brain markers that might predict the efficiency of these treatments.

